#### **Study patients:**

Inclusion criteria:

1. Adults ( $\geq 40$  years) with a primary clinical diagnosis of COPD
2. A post-bronchodilator FEV1/FVC  $< 0.70$  from spirometry performed within the preceding 12 months (no specific FEV1 percent-predicted requirement, although we anticipate the FEV1 will average around 45% of predicted, based on previous studies of pulmonary rehabilitation)
3. The patient was referred to pulmonary rehabilitation
4. The patient is clinically-stable: no exacerbation in preceding 4 weeks
5. Modified Medical Research Council (mMRC) dyspnea rating of at least 2 out of 5.

Exclusion criteria

1. Disease severity or co-morbidity that would make the patient be at-risk for participation this study
2. A significant movement disorder, such as hemiplegia, etc.
3. Inability to read and comprehend the questionnaires, which will be in English
4. A history of poor wound healing or chronic skin conditions that might predispose to local problems from wearing the DynaPort. (The DynaPort can be worn outside a thin garment, such as a tee shirt, and is relatively thin, without protruding parts. However, since the device may be worn overnight, and there is a remote risk of pressure problems, this exclusion criterion was added).

Comments: It is commonly accepted by pulmonary rehabilitation centers that symptoms and functional status limitation are important for referral, not simply FEV1 values. The PI investigators at the various centers will make the clinical decisions as to whether a patient referred to that center has a principal diagnosis of COPD, is clinically stable (basing this decision on recent exacerbation history), and does not have co-morbidity or disease severity or a movement disorder that would make him/her inappropriate for the study. This is the standard procedure of most rehabilitation centers.

### Sample size estimates

Sample size estimates are based on Langer et al. Am J Transpl 2012 and using <http://www.biomath.info/power/ttest.htm>. Patients following lung transplantation were randomized to exercise training or standard care. Walking activity (min/day) from baseline to 12 weeks increased from  $36 \pm 16$  to  $56 \pm 24$  in the treatment group. Assuming a treatment difference, in minutes, of 18 and a SD of 20 and a within-group analysis, an n of ~ 12 would have a power of 0.80 to show this difference. We expect our improvement in walking time with rehabilitation in COPD patients will be less robust. Assuming an increase in activity (minutes per day of walking) of 10 minutes would require an n of 34 to give a power of 0.80, but an improvement of 8 minutes would require 52 patients. Forty evaluable patients appears to be a reasonable number.

Number of subjects: Our goal will be to recruit 40 patients with evaluable data at 12 weeks. Assuming 10 dropouts during rehabilitation, we would need to recruit 50.

Study period: Recruitment over the 6 sites will be over 10 months (~ 40 weeks). Since study follow-up is for 48 weeks per patient, the study will last approximately 84 weeks from first patient in to last patient out.

Activity measurement: We will use the DynaPort MoveMonitor to assess: sedentary activity, upright activity, walking activity, activity intensity, and steps per day. Activity will be measured for 7 consecutive days, 3 days (12 hours per day) minimum. Patients will be asked to wear the devices 24 hours per day, if possible.

### Protocol synopsis:

1. Patients with COPD entering pulmonary rehabilitation at the study sites will be recruited. Each center will be under its own IRB authority.
2. Rehabilitation will be given per usual pulmonary rehabilitation center protocol; there will be no specific changes in COPD medications, including long acting bronchodilators, short-acting bronchodilators, or inhaled corticosteroids. As is typical with pulmonary rehabilitation, these medications will be managed by the patient's health care provider.

3. Standardized, written post-rehabilitation home exercise recommendations will be given to all patients during rehabilitation and upon completion of the program.
4. Baseline testing:
  - a. Collect information on demographics, baseline testing (see below), list comorbidities
  - b. First measurement of physical activity (before starting pulmonary rehabilitation exercise training), within 6 weeks of beginning pulmonary rehabilitation
  - c. Outcomes testing
5. Weeks from study entry: 12, 24, 36, 48:
  - a. Timing:  $\pm$  3 weeks, except for the 12 week visit, which will be after the end of formal pulmonary rehabilitation, and therefore may occur outside of this 3-week window (rationale: to avoid measuring physical activity during pulmonary rehabilitation days)
  - b. Evaluate for adverse events, list concurrent medications.
  - c. Evaluation for Serious Adverse Events: Evaluation for serious adverse events (SAE) will be made at each study visit if the patient is taking a Boehringer Ingelheim drug. If an SAE is identified on a visit, regardless of causal relationship, it will be reported to Boehringer Ingelheim using the Serious Adverse Event Report (SAE) in Non Interventional Studies (NIS) template within 24 hours or the next business day. The following will be the plan of action for SAE assessment and planning:
    - i. Definitions of adverse events
      - a. An adverse event (AE) is defined as any untoward medical occurrence, including an exacerbation of a pre-existing condition, in a patient in a clinical investigation who received a pharmaceutical

product. The event does not necessarily have to have a causal relationship with this treatment.

- b. A serious adverse event (SAE) is defined as any AE which results in death, is immediately life-threatening, results in persistent or significant disability / incapacity, requires or prolongs patient hospitalisation, is a congenital anomaly / birth defect, or is to be deemed serious for any other reason if it is an important medical event when based upon appropriate medical judgement which may jeopardise the patient and may require medical or surgical intervention to prevent one of the other outcomes listed in the above definitions.

2. Patients may be hospitalised for administrative or social reasons during the study (e.g. days on which infusion takes place, long distance from home to site,). These and other hospitalisations planned at the beginning of the study do not need to be reported as a SAE in case they have been reported at screening visit in the source data and have been performed as planned.

- ii. The intensity of the AE should be judged based on the following:
  - Mild: Awareness of sign(s) or symptom(s) which is/are easily tolerated
  - Moderate: Enough discomfort to cause interference with usual activity
  - Severe: Incapacitating or causing inability to work or to perform usual activities

Causal relationship of adverse event: Medical judgment should be used to determine the relationship, considering all relevant factors, including

pattern of reaction, temporal relationship, de-challenge or re-challenge, confounding factors such as concomitant medication, concomitant diseases and relevant history. Assessment of causal relationship should be recorded in the case report forms.

iii. Yes: There is a reasonable causal relationship between the investigational product administered and the AE.

iv. No: There is no reasonable causal relationship between the investigational product administered and the AE.

Worsening of the underlying disease or other pre-existing conditions:  
Worsening of the underlying disease or of other pre-existing conditions will be recorded as an (S)AE in the (e)CRF.

Changes in vital signs, ECG, physical examination, and laboratory test results: Changes in vital signs, ECG, physical examination and laboratory test results will be recorded as an (S)AE in the (e)CRF , if they are judged clinically relevant by the investigator.

Responsibilities for SAE reporting: The Investigators shall report (i.e., from signing the informed consent onwards through the trial defined follow-up period) all SAEs and non-serious AEs which are relevant for a reported SAE by fax or other secure method using BI SAE Form to the BI Unique Entry Point in accordance with timeline specified below.

v. Within five (5) calendar days upon receipt of initial and follow-up SAEs containing at least one fatal or immediately life-threatening event;

vi. Within ten (10) calendar days upon receipt of any other initial and follow-up SAEs.

vii. BIPI Unique Entry Point:

Boehringer Ingelheim Pharmaceuticals, Inc.  
[name]  
[contact]  
E-mail: PV\_global\[contact]

For each adverse event, the investigator will provide the onset date, end date, intensity, treatment required, outcome, seriousness, and action taken with the BI marketed drug. The investigator will determine the expectedness of the BI marketed drug to the AEs as defined in the Listed or BI Drug Information e.g. Investigator's Brochure, Summary of Product Characteristics (SmPC) or Product Information (PI).

- d. Physical activity measurements, each over 7 days
  - e. Outcomes testing
  - f. Scripted exercise at home directions (except 48 week visit)
6. Comments: Three to 5 days of activity testing is considered adequate to capture a particular patient's activity profile (ERS Statement on Physical Activity, submitted for publication). We will accept a minimum of three days of activity measurement for each assessment. Twelve hours per 24 hour day of activity assessment will be considered a day's measurement. Although we will ask patients to wear the devices day and night, we anticipate many will not wear them at night because of inconvenience. Therefore, a requirement of 12 of a potential 16 hours (75% wear-time) appears reasonable. The DynaPort device has an algorithm that determines wear time. If a missing observation occurs over the course of the 48-week study (such as from technical problems, two or more exacerbations in that time block, etc.), we will carry the last observation forward into that missing spot.

Safety considerations: Pulmonary rehabilitation will be performed per usual protocol by centers with considerable experience in providing this intervention. The DynaPort device is registered with the FDA:

<http://www.accessdata.fda.gov/scripts/cdrh/cfdocs/cfrl/rl.cfm?rid=145003>

<http://www.accessdata.fda.gov/scripts/cdrh/cfdocs/cfrl/rl.cfm?lid=386697&lpcd=IKK>

We do not believe this has any significant risk associated with it. Outcomes assessments are standard and will be performed in the pulmonary rehabilitation area by trained personnel.

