### **Design:**

This will be predominately a hypothesis-generating study. Its general design is that of a longitudinal study (without a control group) evaluating directly-measured physical activity in COPD patients who had participated in pulmonary rehabilitation. Activity measurements will be at baseline (before exercise training is started), and at approximately 12, 24, 36, and 48 weeks (+/- 3 weeks at each time period) following pulmonary rehabilitation. There will be no direct change, per protocol, in the patient's pharmacological treatment for COPD (controller or rescue inhaler medication) or other medical problems; this treatment will be directed by the patient's health care provider.

Three distinct types of analysis will be performed:

1. Evaluation of changes in physical activity before and after pulmonary rehabilitation

2. Predictors of baseline physical activity
3. Predictors of *change* in physical activity following pulmonary rehabilitation.

This will be an intent-to-treat analysis, providing patients complete 50% or more of the pulmonary rehabilitation sessions. Those dropping out with less than 50% attendance will be dropped from the study.

Dealing with Exacerbations: It is anticipated that patients will have COPD exacerbations over the course of the study. Since exacerbations themselves affect physical activity, activity testing will be postponed for 2 weeks following the clinical end of the exacerbation. We have determined that physical activity returns to close to baseline by two weeks after the exacerbation (Ehsan et al, A Longitudinal Study Evaluating the Effect of Exacerbations on Physical Activity in Patients with Chronic Obstructive Pulmonary Disease. Annals of American Thoracic Society 2013; 10(6):559-64). If two exacerbations occur within the same time block, testing for that period will not be performed, and the last observation will be carried forward. If a patient is hospitalized for an exacerbation, that patient will be dropped from the study.

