**Hypotheses to be tested:**

Changes in activity following pulmonary rehabilitation

1. Compared with baseline, COPD patients participating in outpatient pulmonary rehabilitation will show an increase in directly-measured physical activity

- (minutes per day of walking activity from the DynaPort) at the  $12 \pm 3$  week assessment. (primary hypothesis)
2. Compared with baseline, COPD patients participating in outpatient pulmonary rehabilitation will show increases in upright activity, activity intensity, steps per day, minutes with METs  $> 2$  (from the DynaPort) after  $24 \pm 3$ ,  $36 \pm 3$  and  $48 \pm 3$  weeks
  3. Exploratory: We will analyze the trajectory of physical activity over the 48 weeks after initiating pulmonary rehabilitation.

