### **Factors Affecting Study Duration:**

1. Each patient will be followed for approximately 48 weeks from the beginning of pulmonary rehabilitation until the last testing day.
2. St. Francis Hospital will be the first to seek IRB approval and begin patient recruitment. We anticipate IRB approval by approximately mid-February 2015 and first patient entry shortly after that date. Each study site will be required to obtain local IRB approval; we anticipate final approval in all 6 centers within 4 months of study initiation at St. Francis Hospital. If St. Francis secures IRB approval and begins recruiting by February 15, 2015, the last site will begin recruiting by approximately June 15, 2015.

3. Each site will be expected to recruit 8-9 patients over 10 months. However, we anticipate total recruitment will be somewhat shorter than 10 months. Recruitment will be competitive, so patient numbers will probably not be identical across centers. However, we will require four study patients, minimum, per center.
4. Assuming that the last patient will be enrolled by October 15, 2015 (4 months after the last center has secured IRB approval), we should have a data lock and analysis by 48 weeks after that date.

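### The follow-up visits run on two clocks that can differ by up to 6 weeks, which affects the exploratory trajectory and slopes but hardly the primary contrast

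*Combined protocol and SAP*

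**What the plan says.** **Time zero.**
- Protocol synopsis, item 5, schedules the visits as "Weeks from study entry: 12, 24, 36, 48". The table of measurements labels Week 0 as the pre-rehabilitation baseline visit.
- Hypothesis 3 uses another origin: "We will analyze the trajectory of physical activity over the 48 weeks after initiating pulmonary rehabilitation".
- Factors Affecting Study Duration, item 1, agrees with hypothesis 3: "Each patient will be followed for approximately 48 weeks from the beginning of pulmonary rehabilitation until the last testing day".
- The Design section has visits up to "48 weeks (+/- 3 weeks at each time period) following pulmonary rehabilitation", without saying whether that means its start or its end.

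**Gap between the origins.** Protocol synopsis, item 4b, allows the baseline activity recording "within 6 weeks of beginning pulmonary rehabilitation".

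**Week 12.** The Design section, hypothesis 1 and the measurement table all give 12 ± 3 weeks. Protocol synopsis, item 5a, applies that window to the visits "except for the 12 week visit, which will be after the end of formal pulmonary rehabilitation, and therefore may occur outside of this 3-week window". It gives a reason (to avoid recording on rehabilitation days) but no outer limit. Separately, after an exacerbation "activity testing will be postponed for 2 weeks following the clinical end of the exacerbation".

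**Analysis.** The Data analysis section plans graphs of activity by visit and slopes where feasible. Item 5 of the hypotheses uses slopes to define responders. No section names elapsed time, or its origin, as an analysis variable. The comment after the measurement table accepts off-window data and shows the spread of visit times only as error bars.

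**Lock.** Factors Affecting Study Duration, item 4, projects from the last enrolment: "we should have a data lock and analysis by 48 weeks after that date".

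**The concern.** Two sites could each follow the text and test the same nominal visit up to 6 weeks apart, one counting from baseline and the other from the first rehabilitation session. The time course is not a side issue here. Hypothesis 3 labels the trajectory exploratory, but the comment closing the Design section names the rate of change in activity as part of the study's main purpose, and slopes feed the responder definition.

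If nominal weeks served as the time axis, the direction of the slope error would depend on the clock followed. Some of the spread in slopes between patients would then reflect scheduling and not response.

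**Working it through.** **1. The plan's own figures.** The sample sizes of 12, 34 and 52 (gains of 18, 10 and 8 minutes, SD 20, power 0.80) reproduce exactly with a paired t-test at two-sided alpha 0.05 (alpha is assumed; the plan does not state it). No visit timing enters, so the clock question leaves them unchanged.

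**2. Distance between the clocks.** Take study entry as the Week 0 baseline and let w be the wait until rehabilitation starts, 0 to 6 weeks (item 4b). At w = 6:
- entry clock, week-12 window: 9 to 15 weeks after entry, or 3 to 9 weeks after rehabilitation starts;
- start clock, week-12 window: 9 to 15 weeks after rehabilitation starts, or 15 to 21 weeks after entry;
- week-48 window, in weeks after entry: 45 to 51 on the entry clock, 51 to 57 on the start clock.

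The largest shift is 6 weeks, equal to the full width of a ±3 window. At w = 0 the clocks agree.

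**3. How late week 12 can be on the entry clock.** The visit must follow the end of rehabilitation. Programme length is not stated; assume 8 to 12 weeks. With w = 6, the programme ends 14 to 18 weeks after entry, so week 12 is late by at least d = 2 to 6 weeks. Only d above 3 needs the item 5a exemption.

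**4. Slope error if nominal weeks were used.** Assume a linear trend from baseline onward.

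*Five visits.* Nominal weeks 0, 12, 24, 36, 48 have mean 24 and deviations −24, −12, 0, 12, 24. The sum of squares is 576 + 144 + 0 + 144 + 576 = 1440.
- Entry clock, only week 12 late by d: fitted/true = (1440 − 12d)/1440 = 1 − d/120. For d = 2, 3, 6: 0.983, 0.975, 0.950.
- Start clock, all four follow-up visits later by w, baseline coded 0: (1440 + 24w)/1440 = 1 + w/60. For w = 3, 6: 1.05, 1.10.

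*Four post-baseline visits.* Deviations from 30 are −18, −6, 6, 18. The sum of squares is 324 + 36 + 36 + 324 = 720.
- Entry clock, week 12 late by d: (720 − 18d)/720 = 1 − d/40. For d = 2, 3, 6: 0.950, 0.925, 0.850.
- Start clock: all four visits move together, so the ratio is 1.00.

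With no wait and a programme of 12 weeks or less, every error above is zero.

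**5. Data lock.** The last patient's week-48 window closes 48 + 3 = 51 weeks after enrolment on the entry clock, and at up to 6 + 48 + 3 = 57 weeks on the start clock. Against the projected 48 weeks, that is 3 and up to 9 weeks later.

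**The case against.** The schedule is more coherent than a list of clashing phrases suggests. Item 5 and the Week 0 row together support baseline as the origin of the visits. The start-of-rehabilitation wording describes an approximate 48-week span, not individual visit dates. Week 12 has a reasoned exception, and the missing outer limit would alone be only a missing detail. This narrows the point. It does not remove it, because the trajectory hypothesis itself is written on the other clock.

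The slope figures are conditional. The plan does not say that nominal weeks will be used, and the error bars show that actual visit times will be known. Linearity also sits awkwardly with the delayed response the protocol expects. If activity stayed flat until the first session and rose linearly afterwards, the start-clock overstatement would vanish and the wait would distort the entry-clock slope instead. The percentages therefore show an order of size and do not predict the error. They are also proportional: under these assumptions a flat course stays flat whatever the coding.

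A reader might infer more than the documents support:
- *That the primary result is compromised.* Item 5a and the measurement table both make week 12 a post-rehabilitation visit, so the before/after comparison keeps its meaning.
- *That data would be cut off at 48 weeks and open visits filled by carrying values forward.* Item 4 is a projection in a section on study duration, and nothing makes it an analysis cut-off.
- *That late week-12 recordings would be discarded and replaced by baseline.* The plan permits such recordings and does not propose to exclude them.
- *That site comparisons would be biased.* None is planned. The narrower possibility, timing differences entering slope-based responder status, remains.

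**Conclusion.** The concern holds in a limited form. The sections give two origins for the same visits, up to 6 weeks apart, and two rules for the week-12 window. The slope analyses have no stated time variable that would make this harmless.

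The consequence is a modest possible bias in exploratory slopes: 2–5% low or up to 10% high over five visits, and 5–15% low over the four post-baseline visits. The upper ends need the maximum 6-week wait, and the largest understatements also need a 12-week programme. All of these figures rest on baseline as study entry, nominal-week coding and a linear trend; the understatements also assume a programme of 8–12 weeks. The primary contrast and the sample size are largely unaffected. The change should still be made, because the time course is a stated aim and the correction costs little.

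**What to change.** - Reconcile the Design section, the hypotheses, the Protocol synopsis, the measurement table and Factors Affecting Study Duration to one time zero and one definition of the week-12 assessment. The definition should say whether and how the ±3 limit applies, and should fit the exacerbation postponement. The choice of schedule is the sponsor's.
- Record the dates on which rehabilitation starts and ends, alongside the date of each activity recording.
- State in Data analysis that trajectory and slopes are fitted on actual elapsed weeks from that time zero, with off-window recordings kept at their actual time. If time zero is the start of rehabilitation, baseline recordings take values of zero or below.
- Describe the projected data lock as following the last patient's last visit window: 51 weeks after last enrolment on the entry clock, up to 57 on the start clock.
- Optionally, repeat the primary contrast on in-window recordings only.

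The cost is protocol wording, a few dates per patient (visit times are already needed for the error bars), a slightly more complex exploratory model, and a projected lock 3–9 weeks later.

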Comment: We will not be altering the pharmacological management of the patient; this study will focus only on the pulmonary rehabilitation component and specifically how it affects physical activity. It is currently almost impossible to carry out a randomized, controlled trial of pulmonary rehabilitation, since the intervention is considered a gold standard of therapy. The within-group analysis without a control group would be feasible and would not raise ethical issues. While this approach (without a control group) limits the strength of conclusions, the primary intent of this analysis is to explore the rate of change in physical activity with pulmonary rehabilitation (realizing that it probably takes longer to improve than exercise capacity) and predictors of response to the intervention.

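### The adverse-event definition and causality item are keyed to a drug the study does not give, so the plan nowhere records whether an event is related to the monitor or the home exercise

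*Combined protocol and SAP*

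**What the plan says.** All references are to the combined protocol and SAP.

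- **What is studied.** The comment under Design says "We will not be altering the pharmacological management of the patient; this study will focus only on the pulmonary rehabilitation component". Protocol synopsis item 2 leaves medication to the patient's own provider and has rehabilitation delivered as each center normally does it.
- **What the study adds.** Patients wear the DynaPort monitor for 7 days at each assessment. The activity measurement paragraph under Sample size estimates says "Patients will be asked to wear the devices 24 hours per day, if possible". Synopsis items 3 and 5f add standardized home exercise instructions.
- **Named device risk.** Exclusion criterion 4 under Study patients explains that "since the device may be worn overnight, and there is a remote risk of pressure problems, this exclusion criterion was added".
- **Adverse-event collection.** Synopsis item 5b asks for adverse events at weeks 12, 24, 36 and 48, with no drug condition and no definition of its own.
- **Definition.** The only definition is in item 5c. It concerns an occurrence "in a patient in a clinical investigation who received a pharmaceutical" product, and adds "The event does not necessarily have to have a causal relationship with this treatment".
- **Causality.** Item 5c also says "Assessment of causal relationship should be recorded in the case report forms". *Yes* means "There is a reasonable causal relationship between the investigational product administered and the AE"; *No* means "There is no reasonable causal relationship between the investigational product administered and the AE".
- **Other event fields.** The later part of item 5c asks, for each event, for the action taken with the company's marketed drug and for expectedness with respect to that drug.

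**The concern.** The safety text appears to have been carried over from a drug trial. Besides the investigational product, it mentions infusion days and de-challenge or re-challenge, none of which belongs to a study of an activity monitor and rehabilitation. The definition and the causality item therefore ask about an exposure the study does not provide and leave out the ones it does.

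At stake is whether the safety data can be read by cause. If several patients develop skin problems under the monitor, or fall while following the home exercise instructions, the plan has no stated field linking those events to the procedure. The safety considerations at the end of the synopsis judge the device to carry no material risk; the relatedness data as specified cannot support or challenge that judgment.

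**Working it through.** No arithmetic applies: the plan gives no safety figure to reproduce. The check sets the definition and the causality item against each possible meaning of the product.

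| Meaning of the product | Who meets the adverse-event definition | Can *Yes* mark harm from the monitor or home exercise? |
|---|---|---|
| Something the study administers | No one, since it administers no drug | No; there is no such product |
| The company's marketed drug | Patients taking that drug | No; the drug did not cause the harm |
| Any drug the patient takes | Patients taking any drug | No; the drug did not cause the harm |

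1. **Definition.** Under all three meanings a patient on no drug is outside it. The most generous meaning, in the last row, includes everyone else.
2. **Causality.** Under all three meanings the two answers concern a drug. Neither says anything about the monitor or the exercise.
3. **Could the monitor count as the product?** A site might try this, but the definition says pharmaceutical and the remaining fields name the company's marketed drug. Both point away from it.
4. **Is there another place for attribution?** Item 5b has no causality question. The table of measurements lists no adverse-event check. Exclusion criterion 4 and the safety considerations mention device risk but set no rule for attributing an event to the device.
5. **Scope.** The serious-event evaluation that opens item 5c is conditional on taking a company drug. For other patients it is unclear whether the definition and the causality item apply at all. Later wording in the same item, on reporting all serious events from consent onward and on the data needed for each adverse event, carries no such condition, so the scope is not settled.

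The documents do not say how many patients will take a company drug, or any drug. Of the 50 to be recruited, the number outside the definition or the serious-event evaluation could in principle be anywhere from 0 to 50. The missing attribution affects all of them, whatever they take.

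**The case against.** The strongest reply is that item 5c is a drug-safety reporting block for patients on a company drug, and that product-based questions suit that purpose even if the wording is poor. Adverse events in general are the business of item 5b, which has no drug condition. The definition needs no causal link, so a skin problem or a fall in a patient taking any drug can be listed. Rehabilitation itself is usual care, and the device risk is called remote and is reduced by an exclusion criterion and by wear over a thin garment.

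Most of this stands. Events are not necessarily lost, and supervised rehabilitation should not be counted as a study-added exposure. But if item 5c is only for company-drug patients, item 5b is left with no definition and no attribution for anyone else. A low expected risk lowers the priority of the gap without closing it.

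Two stronger readings are tempting, and the documents support neither:

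- **That harm from the monitor or exercise must be recorded as unrelated.** *No* means only unrelated to the product, which is a true answer for a pressure sore. It does not deny a link to the monitor.
- **That the data could never show such harm, or that a count of zero related events is guaranteed.** The case report form is not in the documents and may hold further fields. The onset and end dates and treatment required by item 5c could also be compared with the 7-day wear periods.

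**Conclusion.** The point holds as a gap in definition and attribution. As written, the only adverse-event definition leaves out a patient on no drug, and no part of the plan records relatedness to the monitor or to the scripted home exercise. This rests on a literal reading of the definition and on the case report form containing no more than the plan describes.

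No numerical size can be given. The plan states no safety-rate objective and describes the study as mainly hypothesis-generating. The effect is confined to whether adverse events can be summarized by cause; sample size, error rates and the primary week-12 comparison are untouched. It is still worth correcting, because following the stated rules gives an incomplete record for a risk the plan itself names, and the remedy is small.

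**What to change.** 1. **Item 5b:** define an adverse event as any untoward medical event in an enrolled patient from consent onward, whatever drugs the patient takes. Item 5c already uses consent as the start of serious-event reporting, so the two would agree.
2. **Item 5b:** record relatedness as two separate yes/no items, one for the activity monitor and one for exercise.
3. **Item 5c:** keep the drug causality, action-taken and expectedness fields only for patients taking a company drug, and replace the reference to an investigational product there with the company's marketed drug.

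A routine question about skin at the monitor site when each recording ends would be a reasonable addition, but it is optional and the correction does not depend on it.

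The cost is a wording amendment at six sites, each under its own IRB, and two extra case report form items. No visit or analysis changes.
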